6.2.3 Guidelines for dose escalation and determination of MTD and/or RPIID

6.2.3.1 Definitions of MTD and/or RPIID

The MTD for this study is defined to be the highest dose of LDE225 and INC424 not expected to cause dose limiting toxicity (DLT) in more than 35% of patients.

[figure not shown]
The RPIID may be determined to be the same as the MTD or may be lower if the evolving safety profile and other assessments (e.g. PK) suggest a better safety profile without substantial loss of benefit in exposure/potential antitumor activity. The RPIID may also be determined without reaching MTD (e.g. no substantive increases in exposure with increases in dose), if evolving safety and other assessments indicate further increases in dose will result in excessive toxicity without additional benefit.

6.2.3.2 Implementation of dose escalation decisions

A 6-parameter Bayesian Logistic Regression Model (BLRM) for combination treatment will be fitted on the 6-week dose-limiting toxicity data (i.e. absence or presence of DLT) accumulated throughout the dose escalation to model the dose-toxicity relationship of LDE225 and INC424 when given in combination.

The general plan is that cohorts of patients will receive escalating doses of LDE225 or INC424 until the MTD of the combination is reached. Each cohort will consist of newly enrolled patients. The following provides a full description of the algorithm of dose escalation/de-escalation for the study:

- a. A cohort of 3 to 6 evaluable patients will typically be treated at each dose level of LDE225 in combination with INC424.

- b. Patients will be considered evaluable for dose escalation if they have met the minimum treatment and safety evaluation requirements listed below or if they experience a DLT during the first 6 weeks. Patients who do not meet the minimum treatment and safety evaluation requirements provided below will be regarded as ineligible for inclusion in the dose determining set (DDS: see [Section 10.1.3](#)) and additional patients may be enrolled to ensure an adequate number of evaluable patients in each cohort. The minimum treatment and safety evaluation requirements for dose escalation will have been met if:
1. The patient has been treated with at least 75% of the planned doses of LDE225 and INC424 in 6 weeks (42 days) (i.e. no more than 10 missed doses of LDE225 and no more than 20 missed doses of INC424 in 6 weeks are permitted).
 2. The patient has been observed for at least 6 weeks following the first dose, and
 3. The patient has completed sufficient safety evaluations, as agreed by the investigators and the Sponsor, to determine that a DLT did not occur.
- c. After completion of each cohort the BLRM will be used to make recommendations about the next dose level, with the following two exceptions:
- If 2 of the first 2-3 patients in a cohort experience a DLT, further enrollment to that cohort will be suspended. The Bayesian logistic regression model will be updated with this new information before additional patients are enrolled to the study.
 - If a decision is made to escalate to a higher dose level, but one or more additional patient(s) (under the condition e) treated at any previous dose level experiences a DLT in 42 days, then the BRLM will be updated before any additional patient is enrolled to the higher dose level.
- d. Following the principle of EWOC, after completion of each cohort of patients the recommended dose is one among the doses fulfilling EWOC, and typically, the one with the highest posterior probability of the DLT rate falling in the target interval [0.16, 0.35]. Per EWOC it should be unlikely (< 25% posterior probability) that the DLT rate at the dose will induce excessive toxicity [0.35, 1.00]. The maximum dose increments specified in [Section 6.2.2](#) will not be exceeded.
- e. For further understanding of the safety, tolerability and PK of LDE225 and INC424, additional patients may be enrolled at dose levels established to be safe before or while proceeding with further dose escalation.

To determine the dose regimen for the next cohort, the available toxicity information (including adverse events that are not DLTs), PK, PD, and efficacy information, as well as the recommendations from the BLRM will be evaluated by the Investigators and Novartis study personnel (including the study physician and statistician) at a dose decision meeting or teleconference.

Dose escalation will continue until identification of the MTDs and/or RPIIDs. This will occur when the following conditions are met:

1. at least 9 patients have been treated at each MTD and/or RPIID dose,
2. this dose satisfies one of the following conditions:
 - a. the posterior probability of targeted toxicity at this dose exceeds 50%, or
 - b. a minimum of 24 patients have already been treated in Phase Ib.

Drug administration at the next dose level may not proceed until the investigator receives written confirmation from Novartis that the results of the previous dose level were evaluated and it is safe to proceed to a higher dose level. The Dose Determining Set (DDS: See [Section 10.1.3](#)) will be used for the determination of the MTD and/or RPIID.

6.2.4 Dose cohort modification

Provisional dose levels are listed in [Table 6-2](#). Possible changes in dose administration according to the BLRM include but are not limited to:

- a. Expansion of the current dose group to further assess suspected treatment-related adverse events
- b. Administration of a dose below the starting dose for the study
- c. Administration of an intermediate dose between the current and preceding dose
- d. Administration of an intermediate dose between the current and the next planned dose
- e. Termination of any further escalation of study drug

If a decision is made to escalate to a higher dose level, and subsequently additional patient(s) on the lower dose level experiences a DLT in the first 6 weeks of treatment, then further enrollment of patients to the higher current dose will be put on hold until the statistical model has been updated with the new safety information. Enrollment to the higher dose level may be resumed only if it is still recommended by the updated model and considered acceptable following a medical review.

Clinically relevant toxicities will be those assessed as unrelated to disease, disease progression, inter-current illness, or concomitant medications.

Additional patients may be enrolled if the minimum number of evaluable patients required to meet study objectives are not available.

6.2.4.1 Implementation of dose escalation decisions

To implement dose escalation decisions, the available toxicity information (including adverse events and laboratory abnormalities that are not DLTs), the recommendations from the BLRM, and the available PK and PD information will all be evaluated by the Investigators and Novartis study personnel (including the study physician and statistician) during a dose decision meeting by teleconference. Drug administration at the next higher dose level may not proceed until the investigator receives written confirmation from Novartis indicating that the results of the previous dose level were evaluated and that it is permissible to proceed to a higher dose level.

6.2.4.2 Intra-patient dose escalation during Phase Ib

Intra-patient dose escalation is not permitted at any time within the first 24 weeks of study treatment. At Week 25, individual patients on INC424 doses of 10 mg or 15 mg BID may be considered for treatment at one INC424 dose level higher than the dose level to which they were initially assigned, the LDE225 dose must remain constant. Patients may only intra-patient dose escalate by one INC424 level every 4 weeks up to a maximum dose of INC424 20 mg BID. In order for a patient to be treated at a higher dose level of INC424, he or she must have tolerated the initial dose level for at least 24 weeks of therapy (e.g., he or she must

not have previously experienced a toxicity of CTCAE grade ≥ 2 for which relationship to study drug cannot be ruled out). Moreover, the new, higher dose level with which the patient is to be treated must be a dose level that has been declared to be well-tolerated at a dose escalation meeting and does not exceed the MTD.

Consultation with Novartis must occur prior to any intra-patient dose escalation occurring. These changes must be recorded on the Dosage Administration Record CRF.

6.2.5 Definitions of dose limiting toxicities (DLTs)

A dose-limiting toxicity (DLT) is defined as an adverse event or abnormal laboratory value assessed as unrelated to disease progression, inter-current illness, or concomitant medications that meets any of the following criteria in [Table 6-3](#).

For the purpose of dose escalation decisions, only DLTs occurring during the first 6 weeks of study treatment will be necessarily considered and included in the BLRM.

[figure not shown]
Toxicity will be assessed using the NCI Common Terminology Criteria for Adverse Events, version 4.03 (evs.nci.nih.gov/ftp1/CTCAE) unless otherwise specified.

The investigator must notify the Sponsor immediately of any unexpected CTCAE grade ≥ 3 adverse events or laboratory abnormalities. Prior to enrolling patients into a higher dose level, CTCAE grade ≥ 2 adverse events will be reviewed for all patients at the current dose level.

For toxicities which, by definition, require a time-window in order to be defined as DLTs (grade 3 non-hematologic toxicity for ≥ 7 consecutive days), a subsequent visit and/or laboratory assessments must be scheduled accordingly. For example, if a grade 3 non-hematologic toxicity is observed, it must also be observed at least 7 days later, with no intervening lower grades, in order to qualify as a DLT.

Table 6-3 Criteria for defining dose-limiting toxicities

| TOXICITY | DLT CRITERIA |
|---|--|
| Hematologic | |
| Blood and lymphatic system disorders | Neutropenia CTCAE Grade 4* |
| | Febrile neutropenia CTCAE Grade ≥ 3 (ANC $< 1.0 \times 10^9/L$ + Fever ≥ 38.5 degrees C) |
| | Thrombocytopenia CTCAE Grade 4 (Platelets $< 25 \times 10^9/L$)* |
| | Hemorrhagic Event CTCAE Grade ≥ 2 |
| | Anemia CTCAE Grade 4 for ≥ 7 days despite PRBC transfusions |
| Non-Hematologic | |
| Gastrointestinal disorders | Vomiting CTCAE Grade ≥ 3 for > 7 days in duration |
| | Nausea CTCAE Grade 3 despite the use of anti-emetic therapy |
| Hepatic | Total bilirubin CTCAE Grade ≥ 3 , with Direct Bilirubin ≥ 0.5 mg/dL |
| | AST/SGOT or ALT/SGPT CTCAE Grade 3 for ≥ 5 consecutive days |
| | AST/SGOT or ALT/SGPT CTCAE Grade 4 |
| CK elevation | CTCAE Grade ≥ 3 |
| Other | Any CTCAE Grade 3 non-hematologic toxicity for ≥ 7 days Any CTCAE Grade 4 non-hematologic toxicity |
| CTCAE version 4.03 will be used for all grading. | |
| * In two consecutive assessments (the second assessment will be considered valid and final) | |

Appropriate eligibility criteria and specific DLT definitions, as well as specific dose modification and stopping rules are included in this protocol.

Patients who experience a DLT will have their therapy with LDE225 and INC424 interrupted and will be followed as described in [Table 6-4](#). After recovery from the toxicity in question, if the Investigator believes that it is in the patient's best interest to resume therapy with LDE225 and INC424, the patient may resume therapy, only after consultation with the Sponsor, according to the guidelines described in [Section 6.3.1](#) and [Table 6-4](#).

However, the patient must be permanently discontinued from study medication and withdrawn from the study, if any of the following DLTs occur:

- any grade ≥ 3 hemorrhagic event
- grade 4 anemia for ≥ 7 consecutive days despite PRBC transfusions
- 2nd episode of grade ≥ 3 febrile neutropenia
- grade 3 renal toxicity for ≥ 7 consecutive days
- grade 4 renal toxicity
- grade 4 non-hematologic toxicity

If during the first 6 weeks a patient misses > 10 doses of LDE225 or > 20 doses of INC424, the patient will not be evaluable for DLTs. The patient can continue in the study, but another patient has to be enrolled at the same dose level in order to reach the required minimum number of patients in the cohort.

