If a patient requires a dose delay from either study drug of > 21 days due to an LDE225 or INC424 related toxicity, then the patient must be discontinued from the study; however, if the patient is obtaining clinical benefit in terms of response, the patient may continue treatment at the same or at a reduced dose following discussion between the investigator and Novartis. All patients will be followed for AEs and SAEs for 30 days following the last dose of LDE225 and/or INC424.

Dose modifications for toxicities occurring during the DLT-definition period (6 weeks or 42 days) will not be allowed unless the toxicity qualifies as a DLT. After a toxicity has been characterized as a DLT, a patient can resume therapy with a reduced treatment dose according to the guidelines provided in [Section 6.2.5.1](#).

If the administration of study treatment was interrupted for reasons other than toxicity, then treatment with LDE225 and INC424 may be resumed at the same dose.

Patients who experience muscle toxicity, regardless of whether the toxicity meets the criteria described for a DLT, should be followed according to the dosing modifications for LDE225 as per [Table 6-5](#).

Patients who experience hematologic, renal, or hepatic toxicities should receive follow up evaluations as outlined in [Table 6-7](#).

All interruptions or changes to study drug administration must be recorded on the Dosage and Administration Record eCRF.

[figure not shown]

Table 6-4 Criteria for interruption and re-initiation of INC424 and LDE225 treatment

| | |
|--|---|
| Dose modifications for toxicities occurring during the DLT-definition period (6 weeks or 42 days), and considered as treatment-related, will not be allowed until the toxicity qualifies as a DLT. | |
| Worst toxicity (CTCAE 4.03 Grade) | Dose Modifications for INC424 and LDE225 |
| HEMATOLOGICAL | |
| Neutropenia (ANC) (for 2 consecutive assessments within 48 hrs except febrile neutropenia) | |
| Grade 1 (ANC < LLN - $1.5 \times 10^9/L$) Grade 2 (ANC < $1.5 - 1.0 \times 10^9/L$) Grade 3 (ANC < $1.0 - 0.5 \times 10^9/L$) | INC424: Maintain dose level LDE225: Maintain dose level |
| Grade 4 (ANC < $0.5 \times 10^9/L$) | INC424: Hold dose until resolved to \leq grade 1, then maintain dose level LDE225: Hold dose until resolved to \leq grade 1, then maintain dose level |

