| Febrile neutropenia (Grade \geq 3) (ANC < $1.0 \times 10^9/L$, with a single temperature of ≥ 38.3 °C or a sustained temperature of ≥ 38 °C for more than one hour) | INC424: Discontinue study treatment LDE225: Discontinue study treatment |
| Thrombocytopenia (for 2 consecutive assessments within 48 hrs) | |
| Grade 1 (PLT < LLN - $75 \times 10^9/L$) | INC424: Maintain dose level LDE225: Maintain dose level |
| Grade 2 (PLT < $75 - 50 \times 10^9/L$) | INC424: Reduce to 10 mg BID or continue at same dose level (whichever is lower) LDE225: Maintain dose level |
| Grade 3 (PLT < $50-25 \times 10^9/L$) | INC424: Reduce to 5mg BID LDE225: Maintain dose level |
| Grade 4 (PLT < $25 \times 10^9/L$) | INC424: Hold dose until resolved to \leq grade 1, then maintain dose level LDE225: Hold dose until resolved to \leq grade 1, then maintain dose level |
| Hemorrhagic event of any kind (if related to study treatment) | |
| Grade 1 | INC424: Maintain dose level LDE225: Maintain dose level |
| Grade 2 | INC424: Hold dose until resolved completely, then \downarrow by 5 mg BID LDE225: Hold dose until resolved completely, then maintain dose level |
| Grade 3 or 4 | INC424: Discontinue study treatment LDE225: Discontinue study treatment |
| RENAL | |
| Serum creatinine | |
| < 2 x ULN | INC424: Maintain dose level LDE225: Maintain dose level |
| 2 – 3 x ULN | INC424: Hold dose until resolved to \leq grade 1, then: If resolved in \leq 7 days, then maintain dose level If resolved in > 7 days, then \downarrow by 5 mg BID LDE225: Hold dose until resolved to \leq grade 1, then: If resolved in \leq 7 days, then maintain dose level If resolved in > 7 days, then \downarrow 1 dose level |
| Grade 3 (> $3.0 - 6.0 \times ULN$) | INC424: Discontinue study treatment LDE225: Discontinue study treatment |
| Grade 4 (> $6.0 \times ULN$) | INC424: Discontinue study treatment LDE225: Discontinue study treatment |

| | |
|--|---|
| Dose modifications for toxicities occurring during the DLT-definition period (6 weeks or 42 days), and considered as treatment-related, will not be allowed until the toxicity qualifies as a DLT. | |
| Worst toxicity (CTCAE 4.03 Grade) | Dose Modifications for INC424 and LDE225 |
| HEPATIC | |
| Bilirubin (*for patients with Gilbert Syndrome these dose modifications apply to changes in direct bilirubin only). Bilirubin will be fractionated if elevated | |
| Up to 2.0 x ULN | INC424: Maintain dose level LDE225: Maintain dose level |

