7.1.3 Discontinuation of Study Treatment

Patients may voluntarily discontinue from study treatment for any reason at any time. If a patient decides to discontinue from the study treatment, the investigator must make every effort (e.g., telephone, e-mail, letter) to determine the primary reason for this decision and record this information in the patient's chart and on the appropriate eCRF pages. Patients may be considered withdrawn if they state an intention to withdraw, fail to return for visits, or become lost to follow-up for any other reason.

The investigator should discontinue study treatment for a given patient if he/she believes that continuation would be detrimental to the patient's well-being.

Study treatment must be discontinued under the following circumstances:

- Emergence of the following adverse events:
 - Grade 3 or 4 hemorrhagic event of any kind
 - Grade 3 renal toxicity for ≥ 7 consecutive days
 - Grade 4 renal toxicity
 - Grade 4 non-hematologic toxicity
 - Second occurrence of QTcF > 500 ms (\geq Grade 3) or > 60 ms change from baseline on at least two separate ECGs
 - Patient requires or undergoes splenic irradiation
 - Patient requires or undergoes splenectomy
- Any of the following laboratory abnormalities:
 - Grade 4 anemia for ≥ 7 consecutive days despite PRBC transfusions
 - Febrile neutropenia (Grade ≥ 3) (ANC $< 1.0 \times 10^9/L$, with a single temperature of ≥ 38.3 °C or a sustained temperature of ≥ 38 °C for more than one hour)
 - Grade 3 or 4 serum creatinine
 - Bilirubin $> 10.0 \times ULN$
 - Grade 3 or 4 asymptomatic or symptomatic CK elevation with renal function impairment in which CK and creatinine levels do not return to baseline after interrupting treatment
- Pregnancy

- The following deviations from the prescribed dose regimen for LDE225 and INC424:
 - Interruption of study treatment for > 21 days, regardless of reason, from the intended day of the next scheduled dose. However, if the patient is obtaining clinical benefit in terms of response, the patient may continue treatment at the same or at a reduced dose following discussion between the investigator and Novartis.
 - If after 2 dose reductions and after the treatment has resumed at the lower dose, the same toxicity recurs with the same or worse severity (except for thrombocytopenia, anemia, and neutropenia)

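### Febrile neutropenia has unmatched rules in the protocol, so a mandatory stop in the 42-day window can go uncounted as a DLT

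*Protocol*

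**What the plan says.** Four places in the protocol govern Grade 3 or higher febrile neutropenia.

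- **DLT definition (6.2.5, Table 6-3).** ANC below 1.0 x10^9/L with fever of at least "38.5 degrees C".
- **Stopping rule (6.3.1, Table 6-4, and 7.1.3).** Table 6-4 describes the event as the same ANC "with a single temperature of ≥ 38.3 °C or a sustained temperature of" at least 38 °C for more than an hour, and discontinues both drugs. Section 7.1.3 repeats this definition ("with a single temperature of" at least 38.3 °C, or the sustained alternative) under the lead-in "Study treatment must be discontinued under the following circumstances". It makes no exception for the DLT window.
- **Permanent discontinuation after a DLT (6.2.5).** The list includes only the "2nd episode of grade ≥ 3 febrile neutropenia".
- **Dose changes in the first 42 days.** Section 6.3.1 says that modifications for toxicity "will not be allowed unless the toxicity qualifies as a DLT". The Table 6-4 header says that they "will not be allowed until the toxicity qualifies as a DLT".

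The DDS (Protocol 10.1.3, SAP 2.2.3) admits patients who received at least 75% of planned doses and have sufficient safety evaluations, or who stopped early because of a DLT. Under 6.2.5, a patient who misses more than 10 LDE225 or more than 20 INC424 doses is not evaluable, and "another patient has to be enrolled at the same dose level" to reach the cohort minimum. The replacement policy in 7.1.3.1 also ties further enrolment to that minimum.

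**The concern.** The Bayesian logistic regression model (BLRM) and its overdose check use only DDS patients and DLTs as defined in Table 6-3. If the protocol orders a stop for an event that Table 6-3 does not recognise, the model either loses that patient or records the dose as tolerated. Either way the input leans toward safety, and the DLT listing understates toxicity in the same direction.

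Sites also face two direct conflicts. Inside the window, 7.1.3 requires a stop that 6.3.1 and the Table 6-4 header appear to forbid when the event is not a DLT. For an event that is a DLT, 6.2.5 reserves permanent discontinuation for the second episode, whereas Table 6-4 (to which 6.2.5 sends the reader for resumption) and 7.1.3 require it at the first. This second conflict does not change what is counted. It concerns the same named event and can be corrected at the same time.

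**Working it through.** The plan gives no figure that depends on the fever threshold, so there is nothing to reproduce. The check has four parts.

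**1. Who falls in the gap.** Confirmed Grade 4 neutropenia (ANC below 0.5) is a DLT at any temperature. The remaining range is ANC 0.5 to below 1.0, with a single temperature of 38.3 to below 38.5 °C, or 38.0 to below 38.5 °C sustained for over an hour, and not attributed to intercurrent illness. The catch-all rows of Table 6-3 cover only non-hematologic toxicity. CTCAE grading does not close the gap, because 6.2.5 applies CTCAE unless otherwise specified and Table 6-3 specifies 38.5 °C.

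**2. What happens to that patient.** Planned doses in 42 days are 42 of LDE225 and 84 of INC424. Assume full dosing up to the stop.

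| Last dose | Missed LDE225 | Missed INC424 | Result |
|---|---|---|---|
| Day 31 | 42 − 31 = 11 | 22 | Fails (limits 10 and 20); out of the DDS |
| Day 32 | 42 − 32 = 10 | 20 | Meets the rule; in the DDS without a DLT, if otherwise evaluable |

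A last dose by day 31 therefore removes the patient, and one on days 32–41 scores the patient as tolerating the dose.

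**3. How often.** Protocol 1.4.2.2.1 reports, for the ruxolitinib phase III studies, discontinuation for neutropenia in 0.3% of patients. It gives a median onset of Grade 3 or 4 neutropenia of 12 weeks. The Amendment 2 rationale reports 30 Phase Ib patients treated. Assume that these rates carry over to the combination and that onset is exponential:

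- share with onset by week 6: 1 − 0.5^(6/12) = 0.293;
- expected neutropenia stops by week 6: 30 × 0.003 × 0.293 = 0.026, about 0.03.

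The gap case is only a part of these.

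**4. Effect on the overdose check if it happened.** I used the protocol's six-parameter BLRM with the Table 10-1 priors, reference doses of 30 mg/day INC424 and 700 mg LDE225, and importance sampling from the prior. The limit is a posterior probability below 0.25 that the DLT rate is at least 35%. Cohort results and platelet mix are assumptions.

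First escalation step: probability at INC424 15 mg BID + LDE225 400 mg, given the results at 10 mg BID + 400 mg:

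| Cohort 1 | Platelets >200 | Platelets ≤200 |
|---|---|---|
| 0/3 (event uncounted) | 0.106 | 0.147 |
| 1/4 (excluded patient counted) | 0.270 | 0.342 |
| 1/5 | 0.224 | 0.282 |
| 1/6 | 0.187 | 0.233 |

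Step to 20 mg BID + 400 mg, platelets >200, with 2/9 DLTs at 15 mg BID + 400 mg as reported in the Amendment 1 rationale:

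| Assumed cohort 1 | 2/9 | 3/10 (excluded patient counted) | 3/9 (late stopper counted) |
|---|---|---|---|
| 0/3 | 0.242 | 0.414 | 0.473 |
| 0/6 | 0.197 | 0.355 | 0.407 |

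These figures describe first entry to 20 mg BID. Declaring the dose required at least nine patients treated at it (6.2.3.2). If 1/9 DLTs is assumed there, with cohort 1 at 0/3 and platelets >200, the probability at 20 mg BID + 400 mg is 0.04 with 2/9 at 15 mg BID and 0.09 with 3/10. Both are well under 0.25.

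**The case against.** The strongest reply is that a DLT definition and a stopping rule do different jobs and need not match. One feeds the model and the other protects the patient. The protocol separates them elsewhere: Grade 2 hemorrhage is a DLT but leads only to a hold and reduction, and Grade 3 creatinine means discontinuation, although a Grade 3 non-hematologic toxicity must last seven days to be a DLT. That is fair, and different thresholds alone would not be an error. It does not explain why one named event has different definitions, different episode counts and a window restriction that contradicts a mandatory stop.

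An uncounted event would also still be seen. Adverse events of Grade 2 or above are reviewed before a higher dose opens (6.2.5), and non-DLT toxicity is weighed at dose meetings (6.2.3.2, 6.2.4.1). This softens the consequence, but neither review enters the BLRM.

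A reader might go further than the documents allow in three ways.

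- **That the gap is a realistic frequency.** Using the 1.3% of patients whose dose was held or reduced for neutropenia, with the planned 36 patients, gives 36 × 0.013 × 0.293 = 0.14. The concern is a stop, for which the same section gives 0.3%, and 30 patients were treated.
- **That every such patient is replaced.** Further enrolment depends on the cohort being below its minimum.
- **That the chosen dose is unsafe or that a DLT was missed.** No gap case is reported, the crossing of 0.25 needs an assumed event and assumed cohort data, and larger first cohorts (1/5 and 1/6 with platelets >200) do not cross it.

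**Conclusion.** The inconsistency is real and follows from the text alone. For one narrow presentation, the plan orders a toxicity stop and then omits it from the DLT count, always in the direction of apparent safety. The severity is minor. The expected number of neutropenia stops by week 6 is about 0.03, which rests on ruxolitinib monotherapy rates and exponential onset, and the gap case is rarer still. A single event could have changed one escalation check under assumed cohort results. It would probably not have overturned the Phase II dose, on the assumption of 1/9 DLTs at that dose. The documents give neither the cohort 1 results nor the platelet mix, so the model figures are illustrations. With the dose confirmed (Amendment 2 rationale) and no Stage 2 enrolment (SAP 1.1), what remains is protocol consistency and the accuracy of the DDS and DLT listing.

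**What to change.** 1. In Table 6-3, replace the febrile neutropenia criterion with the definition in 7.1.3 and Table 6-4: ANC below 1.0 x10^9/L with one temperature of at least 38.3 °C, or at least 38 °C for over an hour. The existing DDS wording then keeps these patients as DLTs.
2. In the 6.2.5 permanent discontinuation list, change the second episode to the first.
3. In 6.3.1 and the Table 6-4 header, exempt discontinuations that 7.1.3 makes mandatory.
4. For the CSR, compare Phase Ib patients excluded from the DDS, and any stopped for febrile neutropenia without a DLT, with the aligned rule. Report any reclassification as a sensitivity DLT listing and BLRM run.

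The cost is a few wording edits and a review of a handful of patients. The review has a limit: scheduled temperatures are taken only at visits, so a sustained fever may not be recoverable from study data. The reported DLT rate may become slightly less favourable. In this trial the edits change no future dose decision.
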